Protocol Synopsis – Public Summary Version

For: NCT06381986

A Clinical Study on the Safety and Efficacy of SHJ002 Sterile Ophthalmic Solution in the Treatment of Corneal Erosion in Patients with Sjogren's Syndrome

Sponsor: Sunhawk Vision Biotech, Inc.

IRB Approval Date: December 16, 2024

Document Date: December 16, 2024 (Final IRB-approved version: Protocol v2.0, dated October 30, 2024)

1. Study Objectives

Primary Objective:

To evaluate the efficacy of SHJ002 ophthalmic solution in reducing corneal fluorescein staining in patients with corneal erosion secondary to Sjogren's Syndrome.

Secondary Objectives:

To assess changes in regional fluorescein staining (iCFS) and patient-reported symptoms using the SANDE questionnaire.

2. Study Design

Design: Multicenter, double-blinded, randomized, vehicle-controlled, parallel-group Phase 2 trial

Participants: Adults ≥ 18 years with Sjogren's Syndrome and corneal erosion

Randomization: 1:1 ratio to SHJ002 or vehicle group

Treatment: One drop per eye, twice daily for 12 weeks

Sites: Multiple hospitals in Taiwan

3. Endpoints

Primary Endpoint:

Change from Baseline to Week 12 in Total Corneal Fluorescein Staining (NEI Scale, score range 0–15; higher scores indicate more severe staining)

Secondary Endpoints:

- Change in Inferior Corneal Fluorescein Staining (iCFS) Score by NEI Scale (0–3 per region; higher scores = worse outcome)

- Change in Symptom Assessment in Dry Eye (SANDE) score (0–100 scale; higher = worse symptoms)

4. Inclusion / Exclusion Criteria

Key Inclusion:

- Adults ≥ 18 years
- Diagnosed with Sjogren's Syndrome and corneal erosion
- Negative pregnancy test for women of childbearing potential

Key Exclusion:

- Ocular diseases other than corneal erosion/DED
- Recent ocular surgery
- Conflicting medication use or other interfering conditions

5. Statistical Analysis Overview

Primary Efficacy Analysis:

Mixed Model for Repeated Measures (MMRM) used to analyze change in CFS from baseline, with covariates including treatment, visit, interaction, and baseline score.

Reporting:

Least squares means (LSM), standard error (SE), 95% confidence intervals (CI), and treatment group comparisons with p-values.

Missing Data:

Assumed Missing at Random (MAR); no imputation was needed.

This is a summary protocol document prepared specifically for public registration purposes on ClinicalTrials.gov. Proprietary scientific or commercial details have been redacted.

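### Does the trial lack a safety answer because its public synopsis names safety only in the title?

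*Combined protocol and SAP*

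**What the plan says.** The title names two subjects: "A Clinical Study on the Safety and Efficacy of SHJ002 Sterile Ophthalmic Solution". From there on the synopsis speaks only of efficacy.

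- Section 1, primary objective: "To evaluate the efficacy of SHJ002 ophthalmic solution in reducing corneal fluorescein staining".
- Section 1, secondary objectives: "To assess changes in regional fluorescein staining (iCFS) and patient-reported symptoms using the SANDE questionnaire".
- Section 3, primary endpoint: "Change from Baseline to Week 12 in Total Corneal Fluorescein Staining".
- Section 3, secondary endpoints: "Change in Inferior Corneal Fluorescein Staining (iCFS) Score by NEI Scale" and "Change in Symptom Assessment in Dry Eye (SANDE) score".
- Section 5, analysis: "Mixed Model for Repeated Measures (MMRM) used to analyze change in CFS from baseline".
- Section 5, reporting: "Least squares means (LSM), standard error (SE), 95% confidence intervals (CI), and treatment group comparisons with p-values".

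The heading and closing note describe the text as a summary made for the public registry, and the front matter identifies Protocol v2.0 of October 30, 2024 as the version the IRB approved. The closing note says that proprietary material was removed.

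**The concern.** Read literally, the title asks two questions and the body plans for one. No adverse-event outcome, tolerability measure, safety population or between-arm safety summary is named. Someone who followed Sections 1, 3 and 5 to the letter would produce no safety result.

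That would matter. The trial is randomized, double-blinded and vehicle-controlled, with twice-daily dosing for 12 weeks in patients whose corneas are already damaged. Drug, vehicle and disease could each cause ocular events, and the concurrent vehicle arm is the means of telling them apart. If no safety outcome were fixed in advance, the choice of what to report could also follow the results.

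**Working it through.** No safety figure is stated, so there is none to reproduce. The check is of content, followed by a test of how much the silence can prove.

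**Step 1. Count the safety items.**

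| Place | Items listed | Safety items |
|---|---|---|
| Section 1, objectives | 2 statements (1 primary, 1 secondary) | 0 |
| Section 3, endpoints | 3 (total staining, inferior staining, SANDE) | 0 |
| Section 5, analyses | 1 (model for staining) | 0 |

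The pregnancy test in Section 4 is an eligibility criterion, not an outcome. A worsening staining or SANDE score might hint at local harm, but both are defined as efficacy measures, and a mean change does not count patients with an event. The factual observation is therefore correct.

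**Step 2. Ask whether Section 5 is complete enough for an omission to mean anything.** Its heading calls it an overview, and its single analysis is labelled as the primary efficacy one, which leaves room for others. SANDE, a listed secondary endpoint, has no analysis described. Inferior staining has none either, unless the reference to CFS is read broadly. There is no sample size, no significance level and no analysis population even for efficacy. A section that leaves out these items for its own listed endpoints has been condensed, so the absence of a safety population or safety tables does not show that none were planned.

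**Step 3. Ask whether a numerical size can be attached.** One could compute the upper bound on an event rate after zero events in n treated patients. The documents give no arm size, so n = 30, 50 and 75 are assumptions.

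- One-sided 95% bound, 1 − 0.05^(1/n): 9.5%, 5.8%, 3.9%.
- Upper limit of the two-sided exact 95% interval, 1 − 0.025^(1/n): 11.6%, 7.1%, 4.8%.

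These values depend on n alone. They would be identical with a full written safety plan and with none, so they do not measure the gap. They are also single-arm rates, whereas the worry is about a comparison between arms.

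**Step 4. Ask what an analyst would do.** If adverse events are recorded, the usual output is the number and percentage of treated patients with an event, by arm. Randomization and the vehicle control make that comparison available whether or not the synopsis lists it as an endpoint. Writing it into the synopsis would describe those tables without altering them.

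**The case for a change.** The best case for acting is that removal of proprietary material does not explain the gap. A line naming adverse events as an outcome is neither proprietary science nor a commercial detail, and no blacked-out text or break appears in Sections 1, 3 or 5. Only the eligibility lists are marked as key items; the objective and endpoint lists carry no such limit. The document exists to inform the public, who are told that safety is studied and cannot see how.

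Much of this stands as a remark on the synopsis. Redaction is indeed a poor explanation, and the objective and endpoint lists are stronger evidence than Section 5. But condensation explains the gap well, and those lists sit inside the same summary. The argument supports saying that this text describes no safety outcome. It does not support saying that Protocol v2.0 has none.

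The worry about selective reporting also stands in principle, but new wording here would do little to cure it. Section 5 speaks of imputation in the past tense, which suggests that data may already have been examined when the text was written. A safety endpoint first added at that stage would not be prespecified and would need to be dated and labelled as such. Any real protection has to lie in Protocol v2.0.

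**Conclusion.** The title and the body of the public synopsis do not match: 0 safety items among 2 objective statements, 3 endpoints and 1 analysis. This is missing detail in a summary. No stated rule or figure is wrong, no efficacy estimate or test changes, and the gap is one that analysts fill with standard adverse-event tables by arm.

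The conclusion rests on two assumptions: that adverse events are being recorded, and that Protocol v2.0 deals with safety in the usual way. The synopsis confirms neither, and the sponsor could settle both by pointing to the relevant sections of the full protocol. If that protocol had no safety assessments at all, the matter would be substantive, but nothing here shows that. No change to the plan follows.

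### Does the summary's silence on which eye supplies the 0–15 staining score leave the primary analysis undefined?

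*Combined protocol and SAP*

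**What the plan says.** Section 2 describes a 1:1 randomised, parallel-group, vehicle-controlled Phase 2 trial and gives the treatment as "One drop per eye, twice daily for 12 weeks". Section 3 puts the primary staining score on the "NEI Scale, score range 0–15; higher scores indicate more severe staining". It lists the inferior-region score as a secondary endpoint, scored "0–3 per region; higher scores = worse outcome". Section 4 states the entry condition for the patient, with no qualifying eye: "Diagnosed with Sjogren's Syndrome and corneal erosion". Section 5 names the analysis: "Mixed Model for Repeated Measures (MMRM) used to analyze change in CFS from baseline". Its covariates are introduced as a non-exhaustive list of treatment, visit, their interaction and baseline score.

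No section mentions a study eye, a worse eye, an average of two eyes, an eye effect in the model or a between-eye covariance. The closing statement describes the document as a summary made for public registration and adds: "Proprietary scientific or commercial details have been redacted".

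**The concern.** In a trial that treats both eyes, the eye rule is part of the definition of the outcome variable. Without it, a reader cannot tell whether the treatment difference refers to a chosen eye or to the patient's average, or how many records each patient contributes. That matters in three ways.

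- Two legitimate rules can give different p-values on the same data.
- If the choice between them were made after seeing results, the false-positive rate would exceed the nominal level.
- If both eyes were entered as though they came from different patients, the standard error would be too small and the primary test too liberal.

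Section 5 is partly in the past tense, for example "no imputation was needed". That suggests data may have been in hand when the summary was worded, so it is reasonable to ask when the rule was fixed.

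**Working it through.** The summary gives no sample size, alpha, power, effect size, standard deviation or between-eye correlation, so it contains no figure to reproduce. From section 3 come the total range (0–15) and the regional range (0–3). Everything else below is assumed: two-sided 5% tests, a between-eye correlation ρ of the change in staining of 0.5, 0.7 or 0.8, equal variance in the two eyes, and a normal approximation for a single comparison at Week 12. This is simpler than the planned repeated-measures model.

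**1. What the scale settles.** 15/3 = 5 regions, the score of one eye. A two-eye sum would run to 2 × 15 = 30, so it is excluded. A study (or worse) eye, a two-eye mean, and both eyes as separate records all stay within 0–15.

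**2. Study eye against two-eye mean.** Each gives one value per patient at each visit, so each keeps its nominal level. Simulated t-tests (20,000 runs; 30, 50 and 80 patients per arm) gave type I error between 4.7% and 5.2%. The variance of the mean relative to one eye is (1 + ρ)/2.

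To size the difference, set the effect so that one eye has 80% power. The expected test statistic is then 1.960 + 0.842 = 2.802 for one eye and 2.802/√((1 + ρ)/2) for the mean. The correlation between the two statistics is √((1 + ρ)/2).

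| ρ | Variance ratio | Expected statistic, mean | Power, mean | Only mean significant | Only one eye significant |
|---|---|---|---|---|---|
| 0.5 | 0.75 | 3.235 | 90% | 11.2% | 1.3% |
| 0.7 | 0.85 | 3.039 | 86% | 7.6% | 1.7% |
| 0.8 | 0.90 | 2.953 | 84% | 5.7% | 1.7% |

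The two rules disagree on significance in 11.2 + 1.3 = 12.5%, 7.6 + 1.7 = 9.3% and 5.7 + 1.7 = 7.4% of trials. Most of that is the extra power of the mean. The reverse case is 1.7% or less.

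**3. Free choice between the two after seeing results.** With no treatment effect, the chance that at least one of the two tests is significant is 7.3%, 6.8% and 6.5% for ρ = 0.5, 0.7 and 0.8. This applies only if the choice was left open until the results were known.

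**4. Both eyes as independent records.** The true standard error exceeds the reported one by a factor √(1 + ρ), so the actual type I error is 2 × (1 − Φ(1.96/√(1 + ρ))):

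- ρ = 0.5: 1.96/1.225 = 1.600, error 11.0%
- ρ = 0.7: 1.96/1.304 = 1.503, error 13.3%
- ρ = 0.8: 1.96/1.342 = 1.461, error 14.4%

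This is the only reading that breaks the test. It requires two records per patient and a model that ignores their correlation. If the model includes the within-patient eye correlation, the problem goes away.

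**5. What the text supports.** Section 2 assigns participants to parallel groups, section 3 uses a one-eye scale, and section 5 names no eye factor. One value per patient fits all three. Nothing stated points to independent eye records or to a choice made on results.

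**The case for a change.** The best case for acting is that the eye rule is not a minor detail and would cost a sentence or two to state. The summary has room for scale ranges, score direction and model covariates. The stated reason for redaction is proprietary content, and which eye is analysed is hardly that. Sections 3 and 5 show no visible redaction mark either. The two-eye mean and the study eye can disagree in about 7% to 13% of trials, and a rule with a date would remove any suspicion that it was picked late.

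Part of this stands. The public text does omit the rule, for both the total and the inferior-region score, and a reader who wants to interpret the estimate exactly needs it.

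The rest does not carry over to the plan. The document calls itself a public summary, labels section 4 as key criteria and section 5 as an overview, and also omits the sample size, alpha, visit schedule and covariance structure. At that level of detail, a missing eye rule says little about Protocol v2.0 or its analysis plan. Past-tense wording dates the summary, not the rule. The trial is Phase 2 and the summary claims no confirmatory status. Reporting several eye rules side by side would make sense only if no rule had been set and both eyes had been scored, and the document shows neither.

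**Conclusion.** No change to the plan follows. The narrow observation is correct: the public summary does not say which eye or eyes supply the staining scores. It is a gap in a condensed document, and the analysis rule is probably in the full protocol or its SAP; that is a judgement, because neither is available here. No stated rule produces a wrong result.

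Between the two ordinary ways of filling the gap, the false-positive rate stays at about 5% and the practical difference is 4 to 10 percentage points of power (84% to 90% against 80%), assuming a between-eye correlation of 0.5 to 0.8. The 11.0% to 14.4% error rate belongs to an analysis that the text does not describe and should not be held against this trial. Two things would alter this view: evidence that both eyes were entered as independent records, or evidence that the eye rule was chosen after the results were seen. The document contains neither.

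### Does the lack of a named visit and test order for iCFS and SANDE leave the trial open to a false secondary claim?

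*Combined protocol and SAP*

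**What the plan says.** Section 3 gives one primary endpoint with its time point: "Change from Baseline to Week 12 in Total Corneal Fluorescein Staining". The secondary endpoints are "Change in Inferior Corneal Fluorescein Staining (iCFS) Score by NEI Scale" and "Change in Symptom Assessment in Dry Eye (SANDE) score", neither with a visit.

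Section 5, under its heading for the primary efficacy analysis, describes a mixed model for repeated measures "used to analyze change in CFS from baseline", "with covariates including treatment, visit, interaction, and baseline score". The line on reporting then lists "Least squares means (LSM), standard error (SE), 95% confidence intervals (CI), and treatment group comparisons with p-values". It names no alpha, no order of testing and no multiplicity rule, and it does not say at which visit the treatment contrast is taken.

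Two other parts matter. Section 2 randomises "1:1 ratio to SHJ002 or vehicle group", so each endpoint at each visit has a single between-group comparison. The title and closing note say that the document is an abridged public version, prepared for a registry and with details redacted. It refers to a full protocol, version 2.0.

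**The concern.** A model with treatment, visit and their interaction can give a treatment contrast at every visit. Section 5 promises p-values without saying which one decides, and the secondary endpoints could be met, on their wording, by a change at any visit. A reader of the results could not tell from this text whether a significant iCFS or SANDE p-value was the planned one or the most favourable of several. Nothing in the text rules out presenting it as a success when the primary has failed.

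iCFS adds a second worry. The total score runs to 15 and each region to 3, so the total has 15 / 3 = 5 regions and iCFS is one of them. A positive iCFS result beside a positive total could be taken for separate confirmation when it is partly the same measurement.

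**Working it through.** **Is the primary contrast undefined?** Set the sections side by side. Section 3 gives one variable (total staining) at one time (Week 12). Section 2 gives two arms. Section 5 places the model under the primary analysis, so CFS there means the primary endpoint. Together they leave one test: the Week 12 difference in least squares means for total staining. Section 5 merely does not repeat the visit. An error of 11% to 13% can be computed for total staining at any of three visits, but it describes a reading that Section 3 excludes.

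**How large is the risk for the secondaries?** The document states no alpha, visit count, correlation or error rate, so it has no figure to reproduce. Inputs:

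- From the document: two secondary endpoints and one two-arm comparison each.
- Assumed: two-sided alpha 0.05 (suggested by the 95% intervals), 1 to 6 post-baseline visits, various correlations, no true effect on anything, and no gating on the primary.

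For k independent tests:

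- Significant in either direction: 1 − 0.95^k
- Significant in favour of SHJ002: 1 − 0.975^k

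Two endpoints at one visit (k = 2):

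- Either direction: 1 − 0.95² = 9.75%
- Favouring SHJ002: 1 − 0.975² = 4.94%

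Two endpoints at three visits (k = 6), independent:

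- Either direction: 1 − 0.95⁶ = 26.5%
- Favouring SHJ002: 1 − 0.975⁶ = 14.1%

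Real endpoints and visits are correlated, which lowers these figures. A multivariate normal simulation (300,000 draws per setting) used correlations of 0 to 0.8 between endpoints and 0 to 0.8 between visits:

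| Visits | Either direction | Favouring SHJ002 |
|---|---|---|
| 1 | 7.8% to 9.7% | 3.9% to 4.9% |
| 2 | 12.0% to 18.6% | 6.0% to 9.7% |
| 3 | 14.9% to 26.5% | 7.5% to 14.2% |
| 4 | 17.3% to 33.7% | 8.6% to 18.4% |
| 6 | 20.7% to 46.0% | 10.4% to 26.2% |

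At three visits, a between-visit correlation of 0.5 to 0.7 and independent endpoints, the either-direction rate is 23.5% to 20.7% and the favourable rate 12.2% to 10.7%. A range of about 10% to 24% can thus be reproduced, but it counts results in which SHJ002 looks worse. As the chance of a false success it is about twice too high; the matching range is about 5% to 12%.

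**What do the assumptions carry?** The visit count drives the answer, and the document does not give it. Gating matters as well. If a secondary is claimed only when the primary is significant, then with no effect on anything the chance of any claim cannot exceed 5% (2.5% in favour of SHJ002). If SHJ002 truly affects total staining but neither secondary, gating helps less, and the one-visit figure of about 5% in favour is the better guide. The text neither states nor excludes gating.

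**What does the sensible reading give?** Taking both secondaries at Week 12, like the primary, leaves two tests. The chance of a false favourable result is then 3.9% to 4.9%, against 2.5% for a single test.

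**The case for a change.** The strongest case for a change is that it would be cheap and the gap is real. Week 12 is written for the primary and could have been written for the two lines below it. A visit and a test order are hardly commercial secrets, and no redaction mark appears at those lines. Every setting in the table exceeds the rate for a single test. A few sentences fixing Week 12 and a sequence of total staining, iCFS and SANDE would hold the familywise error to 5%, with no loss of primary power and no more patients.

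Part of this stands: the public text names no visit and no order for the secondaries, and naming Week 12 would make it clearer. The rest does not carry the point to a change in the plan, for three reasons.

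- The text does not say that secondaries are tested at every visit, or claimed when the primary fails. The only model described is for corneal staining under the primary analysis. Section 1 reserves the language of efficacy for the primary and speaks of assessing change for the others.
- A fixed sequence is one choice among several. Holm's method or descriptive p-values would serve as well. The sequence would also make iCFS, which overlaps with the primary, the gate to SANDE, the only outcome that is not a staining score.
- The missing-data line is in the past tense, so data may already have been examined. A test order chosen now could be post hoc and would then give little of the protection claimed for it.

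**Conclusion.** No change to the plan is needed. The primary conclusion is sound as specified: one endpoint, one visit, two arms. What remains is an unwritten visit and test order for two supportive endpoints, in an abridged public version of a Phase 2 protocol. An analyst would fill the visit with Week 12, and the full protocol may already do so.

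On that reading, the chance of a false favourable secondary result is about 5% or slightly less. It rises to about 11% to 12% only if three visits are assumed, all are tested without gating, and the correlations are as stated above; more visits would raise it further. These figures measure what selective reporting could do. They do not describe anything the document says will be done. How strictly to control secondary p-values in a trial of this kind is a fair trade-off between protection and the ability to report SANDE in its own right. Readers should treat the secondary p-values as supportive and should not count iCFS as independent confirmation of the total score.

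### Does an MMRM under missing-at-random, with no named sensitivity analysis, leave the Week 12 result exposed?

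*Combined protocol and SAP*

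**What the plan says.** The primary endpoint in section 3 is "Change from Baseline to Week 12 in Total Corneal Fluorescein Staining", scored on the "NEI Scale, score range 0–15; higher scores indicate more severe staining". Section 2 gives the allocation as "1:1 ratio to SHJ002 or vehicle group".

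Section 5, Statistical Analysis Overview, has three short entries:

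- The model for the primary endpoint is described in one line: "Mixed Model for Repeated Measures (MMRM) used to analyze change in CFS from baseline, with covariates including treatment, visit, interaction, and baseline score".
- The outputs to be presented are listed next, and they stop at these: "Least squares means (LSM), standard error (SE), 95% confidence intervals (CI), and treatment group comparisons with p-values".
- On absent scores the section has a single sentence: "Assumed Missing at Random (MAR); no imputation was needed".

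No delta adjustment, tipping-point analysis, reference-based imputation or tabulation of missing scores by arm is named. The closing note limits what the document claims to be: "This is a summary protocol document prepared specifically for public registration purposes on ClinicalTrials.gov". The title block identifies the underlying protocol as v2.0, which is not part of what is posted.

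**The concern.** The primary result is a difference at Week 12, so it depends on what is assumed about patients without a Week 12 score. MAR says that their unseen scores follow the pattern predicted by their own earlier scores, baseline and treatment arm. Observed data cannot confirm this. The usual safeguard is to ask how far the conclusion survives if the assumption fails, and the posted text names no such analysis.

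The missing-data sentence is also ambiguous. It may mean that the model needs no imputation, or that no scores were missing. The first reading leaves the question open and the second removes it.

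Suppose patients who stop SHJ002 do worse at Week 12 than their earlier scores predict, and more so than vehicle dropouts. The estimate would then favour SHJ002, and nothing in the posted outputs would reveal it.

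**Working it through.** The document has no figure to reproduce: it gives no sample size, alpha, SD, effect size or dropout rate. Every input below is therefore an assumption, varied over a range.

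**Bias.** Let dA and dV be the shares missing at Week 12 in the SHJ002 and vehicle arms. Let sA and sV be how many points worse the missing scores are than MAR predicts. Then

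net bias towards SHJ002 = dA × sA − dV × sV.

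**Standard error.** With n per arm, SE = SD × √(1/(n(1 − dA)) + 1/(n(1 − dV))).

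**Type I error.** With no true effect and b = bias/SE, a two-sided 5% normal test rejects with probability Φ(−1.96 + b) + Φ(−1.96 − b).

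For SD 3, n = 50, dA = 0.15 and dV = 0, SE = 3 × √(1/42.5 + 1/50) = 0.626. With sA = 3, the bias is 0.15 × 3 = 0.45, b = 0.45/0.626 = 0.719, and the rejection rate is 0.107 + 0.004 = 0.111.

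| dA | sA | dV | sV | Bias (points) | SE | Type I error |
|---|---|---|---|---|---|---|
| 5% | 1 | 0 | – | 0.05 | 0.608 | 5.1% |
| 5% | 2 | 0 | – | 0.10 | 0.608 | 5.3% |
| 15% | 1 | 0 | – | 0.15 | 0.626 | 5.7% |
| 15% | 2 | 0 | – | 0.30 | 0.626 | 7.7% |
| 15% | 3 | 0 | – | 0.45 | 0.626 | 11.1% |
| 15% | 2 | 15% | 0 | 0.30 | 0.651 | 7.5% |
| 15% | 3 | 15% | 0 | 0.45 | 0.651 | 10.6% |
| 15% | 3 | 15% | 2 | 0.15 | 0.651 | 5.6% |
| 15% | 2 | 15% | 2 | 0 | 0.651 | 5.0% |
| 15% | 1 | 15% | 2 | −0.15 | 0.651 | 5.6% (1.4% in favour of SHJ002) |

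**Range over SD and n.** With the vehicle arm complete, SD 2 to 4 and 30 to 80 per arm, the 5%, 2-point case gives 5.1% to 6.1%. The 15%, 3-point case gives 7.0% (SD 4, n = 30) to 27.6% (SD 2, n = 80). The last figure is an extreme corner. It needs a shift of 3/2 = 1.5 SD beyond what earlier scores predict, 15% dropout, a vehicle arm with no informative dropout, and the smallest SD with the largest n.

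**Does ordinary dropout harm the MMRM?** A simulation used 20,000 runs, one early visit correlated 0.6 with Week 12, and 15% dropout in both arms driven by poor early scores. When earlier scores fully explain dropout, the bias is 0.01 points and the rejection rate 4.8%. Residual shifts of 2 and 3 points in the SHJ002 arm alone give bias of 0.29 and 0.46 and rejection rates of 7.4% and 11.0%, close to the closed-form results. Dropout that follows visibly poor scores therefore does no harm; only the unexplained remainder, and only its difference between arms, matters.

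**What the document supplies to choose among the rows.** Nothing. It gives no dropout rate, no reasons for stopping and no indication of which arm would lose more patients.

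**The case for a change.** The strongest case for acting is that the endpoint rests on an assumption the data cannot verify, that the effect could exceed 10% type I error under inputs that are not absurd, and that a remedy costs a few sentences and leaves the primary analysis alone. The summary found room for a missing-data statement, so it had room for one more line. A sensitivity analysis is not obviously proprietary, so the redaction note does not explain its absence.

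Part of this stands. The silence is real, and the missing-data sentence does not tell the reader whether any Week 12 scores were missing.

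The rest does not carry through to a change:

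- The same table could be attached to any trial with an MMRM primary analysis. It shows what informative dropout can do in general and gives no evidence that it happens here, or in which direction.
- The overview also omits sample size, alpha, analysis sets, the visit schedule and the analysis of the secondary endpoints. A text that brief would be expected to omit sensitivity analyses too, whatever the full protocol holds.
- No sensitivity analysis would test MAR; it could only show the consequences of departing from it. Reference-based imputation would also presuppose a view on outcomes after stopping treatment, and the summary states no estimand.
- Section 5 is written in the past tense, which suggests, without proving, that the analysis had been done. If so, anything added would be post hoc and could not be presented as pre-specified.

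**Conclusion.** The primary method is sound, and following it as written is not shown to give a wrong or worse answer. Under assumed inputs of SD 3 and 50 per arm, departures from MAR move type I error from 5.0% (balanced across arms) to 11.1% (15% dropout and a 3-point shift in the SHJ002 arm only). With at most a 1-point shift in the SHJ002 arm and a complete vehicle arm, it stays between 5.1% and 5.7%. The document does not let a reader say which case applies, and it supports no direction of bias.

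What remains is a gap in a public summary that analysts fill sensibly. A normal results report gives missing Week 12 scores by arm and reason. If the counts are not trivial and the full plan has no such analysis, a tipping-point analysis shifting each arm independently is a familiar supplement, labelled post hoc if done after unblinding. The primary model and its result would be unchanged.

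This conclusion rests on the posted summary alone. Protocol v2.0 and any full SAP were not available and may already cover the point. If no Week 12 scores were missing, the question disappears.
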